11.5 Adverse Events of Special Interest

The following events are considered AEs of special interest based on the route of administration and toxicology profile for viltolarsen:

- Access device complication (for patients with indwelling access devices)
- Urinary protein excretion ≥ 300 mg/day based on a 24-hour urine collection
- Serum cystatin C $\geq 1.5 \times$ baseline, or serum creatinine $\geq 2 \times$ baseline and ≥ 0.3 mg/dL, confirmed with a repeat test within 1 week of the original results (i.e., meets the cystatin C or creatinine criteria for referral to a nephrologist described in [Section 11.12.1](#))
- Any confirmed instances of hematuria or other potentially CS abnormalities on urinalysis

11.6 Disease-Related Signs and Symptoms

Reporting of disease-related or DMD-related signs and symptoms as AEs is based on the investigator's clinical judgment. However, progression of symptoms and signs associated with DMD that is inconsistent with the usual course of the disease should be reported as an AE in the eCRF and source documentation.

11.7 Reporting

11.7.1 Adverse Event Reporting

All AEs occurring during the course of the study (starting from signing informed consent to study completion) will be collected on the AE eCRF. Each AE is to be evaluated for duration,

severity, seriousness, and causal relationship to the IP. For each AE, the following information will be recorded:

- Description of the event (e.g., headache)
- Date of onset
- Date of resolution (or that the event is continuing)
- Action taken as a result of the event
- Seriousness of the event
- Severity of the event
- Outcome of the event
- Investigator's assessment of relationship to IP

A cluster of signs and symptoms that results from a single cause should be reported as a single AE (e.g., fever, elevated WBC, cough, abnormal chest X-ray, etc., can all be reported as "pneumonia").

The investigator will carefully evaluate the comments of the patient and the response to treatment in order that he/she may judge the true nature and severity of the AE. The question of the relationship of AE to IP administration should be determined by the investigator or study physician after thorough consideration of all facts that are available.

CS changes from time of ICF will be documented as AEs on the AE eCRF. CS changes are physical findings that have medical relevance and may result in an alteration in medical care.

11.7.2 Adverse Events of Special Interest Reporting

AEs of special interest should be promptly recorded in the eCRF so that the DSMB and medical monitor are notified. Such events will be reviewed by the DSMB and medical monitor to enable consideration of implications for other patients.

11.7.3 Serious Adverse Event Reporting

All SAEs occurring from the time of informed consent until the follow-up telephone call, 30 days following the last administration of IP, must be reported to the designated CRO within 24 hours of the knowledge of the occurrence. This includes death due to any cause and whether or not the SAE is deemed drug-related or expected. After the 30-day reporting window, any SAE that the investigator considers related to IP must also be reported.

To report the SAE, the investigator is to complete the SAE form electronically in the electronic data capture (EDC) system for the study. If the event meets serious criteria and it is not possible to access the EDC system, the investigator is to send an email, phone, or fax the event to the designated CRO within 24 hours of awareness. When the EDC system becomes available, the SAE information must then be entered within 24 hours of the system becoming available.

The investigator is required to submit SAE reports to the IRB or IEC in accordance with local requirements.

11.8 Serious Adverse Event Follow-up

SAEs will be followed by the site investigator until resolution or until the investigator determines that follow-up is no longer medically necessary.

Follow-up information, or new information regarding an ongoing SAE, must be provided promptly to the CRO within 24 hours of knowledge of the new or follow-up information. The CRO will forward the information to the sponsor and the medical monitor.

11.9 Expedited Reporting

The sponsor must report any suspected adverse reaction to the IP, that is both serious and unexpected, to the US FDA, 21 Code of Federal Regulations 312.32(c)(1)(i), and other national and local health authorities.

The NS Pharma, Inc.-designated CRO is responsible for reporting all relevant information about suspected unexpected serious adverse reactions (SUSARs) that are fatal or life-threatening as soon as possible to the applicable regulatory authorities in all the Member States concerned, and to the Central Ethics Committee, and in any case no later than 7 days after knowledge by the CRO of such a case. All other SUSARs will be reported to the applicable regulatory authorities concerned and to the Central Ethics Committee concerned as soon as possible but within a maximum of 15 days of first knowledge by the sponsor/designee.

The NS Pharma, Inc.-designated CRO will also report any additional expedited safety reports required in accordance with the timelines outlined in country-specific legislation.

The NS Pharma, Inc.-designated CRO will also inform all investigators as required per local regulation. Reports of all applicable SUSARs must be communicated as soon as possible to the

appropriate IRB/IEC and/or reported in accordance with local laws and regulations.

Investigators should file written documentation of IRB/IEC notification for each report to the designated CRO as applicable.

11.10 Monitoring and Follow-up of Adverse Events

Patients who experience AEs will be monitored with relevant clinical assessments and laboratory tests, as determined by the investigator. All follow-up results are to be reported to the medical monitor. Any actions taken and follow-up results must be recorded either on the appropriate page of the eCRF or in appropriate follow-up written correspondence, as well as in the patient's source documentation. Follow-up laboratory results should be filed with the patient's source documentation.

For all AEs that require the patient to be discontinued from the study, relevant clinical assessments and laboratory tests must be repeated at appropriate intervals until final resolution or stabilization of the event(s).

Any AEs that are unresolved at the patient's last AE assessment in the study are followed up by the investigator or designee for as long as medically indicated, but without further recording in the eCRF. The CRO retains the right to request additional information for any patient with ongoing AEs at the end of the study, if judged necessary.

11.11 Pregnancy Reporting

The NS Pharma, Inc.-designated CRO should be notified in the event that a female partner of a patient becomes pregnant at any time after the patient's first dose of IP. Any such pregnancy occurring on-study or within 3 months of the last administration of IP must be reported on a Pregnancy Notification Form. This must be done whether or not an AE has occurred and within 24 hours of awareness of the pregnancy. The information submitted should also include the anticipated date of birth or pregnancy termination.

Written consent is required prior to collecting and reporting any information on a female partner of a patient.

If possible, the investigator should follow the pregnant female partner of the patient until completion of the pregnancy and notify the medical monitor of the outcome within 5 days or as

specified below. The investigator will provide this information as a follow-up to the initial Pregnancy Notification Form.

If the outcome of the pregnancy meets the criteria for immediate classification as an SAE (i.e., spontaneous abortion, stillbirth, neonatal death, or congenital anomaly [including in an aborted fetus]), the investigator should follow the procedures for reporting SAEs (see [Section 11.7.3](#)).

11.12 General Monitoring and Management of Abnormal Clinical Laboratory Findings

It is the investigator's responsibility to review the results of all laboratory tests as they become available and to sign and date the results indicating review. For each laboratory test outside of the laboratory normal range, the investigator must ascertain if this represents a CS change from baseline for the individual patient. The investigator may repeat a laboratory test or request additional tests to verify results of the original laboratory test.

If a laboratory value is determined to be an abnormal and CS change from baseline for the patient, the investigator should determine if it qualifies as an AE, and if so, an appropriate eCRF will be completed. All CS laboratory abnormalities occurring during the study and that were not present at baseline should be followed and evaluated with additional tests if necessary, until diagnosis of the underlying cause, or resolution.

11.12.1 Monitoring of Renal Function and Urine Analyses

All scheduled first morning void urinalyses will include urine dipstick protein to be performed at the site. If first morning void urine dipstick protein $\geq 2+$, UPCr ≥ 0.5 mg/mg, or UPCr $\geq 2 \times$ baseline, a first morning void urine dipstick protein will be repeated within 1 week. If 1 or more of these criteria are met again on the repeat test, a 24-hour urine sample will be collected within 1 week of the results to assess protein and creatinine. If proteinuria on a 24-hour urine sample is ≥ 300 mg/day, the patient will be referred to a nephrologist.

In addition, any instances of hematuria or other potentially CS abnormalities on urinalysis will be confirmed at the following week's visit, or sooner at discretion of the investigator. Confirmed CS treatment-emergent abnormalities will be recorded as AEs and discussed with the medical monitor. Abnormalities will be monitored and evaluated with additional tests or consultations, if necessary, until the underlying cause is determined, or the event is brought to an acceptable resolution. Additional clinical and laboratory information may be collected and documented in

order to better characterize abnormalities and identify etiology and appropriate management. Potential need for interruption or discontinuation of IP should be discussed with the medical monitor and sponsor.

If serum cystatin C $\geq 1.5 \times$ baseline, or if serum creatinine $\geq 2 \times$ baseline and ≥ 0.3 mg/dL, the test will be repeated within 1 week of the results. If either of these criteria are met again on the repeat test, the patient will be referred to a nephrologist.

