9.15.1 Sample Collection, Storage, and Shipping

Each patient will have blood drawn and urine collected for the blood and urine laboratory safety assessments as listed/described in the sections below and the Schedules of Study Assessments (Table 1 and Table 2), including hematology, chemistry, urinalysis, 24-hour urine analysis, urine cytology, anti-dystrophin antibody, anti-viltolarsen antibody, and viral antigen and antibody testing.

Blood draw volumes for patients will be 8.5 to 16 mL per day at Screening, Day 1, Weeks 3, 5, 9, 13, 17, 21, 25, 37, 48, and end of treatment, totaling up to approximately 135.5 mL over the course of the study. No more than 31.0 mL of blood will be drawn in a 4-week period.

For post-Screening urinalyses, patients will collect a first morning void urine sample on the date of the specified visit and bring it to the site according to the Schedules of Study Assessments (Table 1 and Table 2). Analysis of the sample will include urine dipstick protein to be performed at the site. An aliquot will also be sent to the central laboratory for urinalysis (see Table 3 for a list of the laboratory analytes that will be measured for all urinalyses, including the first morning void urinalysis).

If first morning void urine dipstick protein $\geq 2+$, urine protein to creatinine ratio (UPCR) ≥ 0.5 mg/mg, or UPCR $\geq 2 \times$ baseline, a first morning void urine dipstick protein will be repeated

within 1 week. If 1 or more of these criteria are met again on the repeat test, a 24-hour urine sample will be collected within 1 week of the results to assess protein and creatinine. Caregivers will be provided a diary to enter void times during the 24-hour collection period. When obtaining this 24-hour urine, the patient will be asked to urinate in the toilet immediately after waking up on the day of the test. This time will be recorded in the diary as the start time. Directions will be provided for collection throughout the test, and documentation of all subsequent voids will be recorded in the diary through the first sample immediately after awakening on the following morning, as close to 24 hours later as possible. Refer to [Section 11.12.1](#) for additional details on monitoring of renal function and urine analyses.

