If serum cystatin C $\geq 1.5 \times$ baseline, or if serum creatinine $\geq 2 \times$ baseline and ≥ 0.3 mg/dL, the test will be repeated within 1 week of the results. Refer to Section 11.12.1 for additional details on monitoring of renal function and urine analyses.

Samples will be collected by a trained member of the study team unless otherwise noted. All blood and urine samples will be sent to the designated central laboratory for testing unless otherwise noted. The urine cytology samples will be collected predose at the site and sent to a local laboratory for analysis. The procedures for the collection, handling, and shipping of central laboratory samples will be specified in the Laboratory Manual. Clinical laboratory tests are listed in Table 3.

Table 3. Clinical Laboratory Tests

Hematology, Chemistry, Urinalysis (Screening, First Morning Void, and Postdose), 24-Hour Urine Analysis, and Urine Cytology – Safety Labs

- Hematology
 - Red blood cell count
 - Hemoglobin
 - Hematocrit
 - Reticulocyte count
 - Mean corpuscular volume
 - Mean corpuscular hemoglobin
 - Mean corpuscular hemoglobin concentration
 - WBC
 - White blood cell differential
 - Platelet count
 - Fibrinogen
 - Activated partial thromboplastin time

-
- Prothrombin international normalization ratio
 - Blood Chemistry
 - Sodium
 - Potassium
 - Chloride
 - Calcium
 - Inorganic phosphorus
 - BUN
 - Creatinine
 - Cystatin C
 - Aspartate aminotransferase
 - Alanine aminotransferase
 - Gamma-glutamyl transferase
 - Alkaline phosphatase
 - Haptoglobin
 - Lactate dehydrogenase/lactate dehydrogenase isozyme
 - Creatine kinase
 - Total bilirubin (direct/indirect)
 - Total protein
 - Albumin
 - Albumin to globulin ratio
 - Total cholesterol
 - Triglyceride
 - Blood glucose
 - C-reactive protein
 - Urinalysis (Screening, First Morning Void, and Postdose)
 - Glucose
 - Blood
 - Urobilinogen
 - Specific gravity
 - Osmolality
 - Urinary sediment (erythrocytes, white blood cells, casts, epithelium, crystals)
 - Protein (benzethonium chloride method)
 - Microalbumin
 - N-acetyl-beta-D-glucosaminidase
 - α 1-microglobulin
 - β 2-microglobulin
 - Creatinine
 - Protein to creatinine ratio
 - Protein osmolality ratio
 - Dipstick protein (to be performed by the site on the first morning void urine samples)
 - 24-Hour Urine Analysis
 - Protein (benzethonium chloride method)
 - Creatinine
-

- Urine cytology

BUN = blood urea nitrogen; WBC = white blood cell count.

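### The proteinuria confirmation rule names only a dipstick as the repeat test, although two of its three criteria are UPCR limits, so it does not clearly mandate a 24-hour collection when UPCR alone stays raised

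*Combined protocol and SAP*

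**What the plan says.** The rule appears in the same form in protocol Sections 9.15.1 and 11.12.1. Any one of three findings on a first morning void starts it: dipstick protein at or above 2+, UPCR at or above 0.5 mg/mg, or UPCR at or above twice baseline.

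- **Repeat step, Section 11.12.1:** "a first morning void urine dipstick protein will be repeated within 1 week. If 1 or more of these criteria are met again", the 24-hour collection follows.
- **Same step, Section 9.15.1:** "If 1 or more of these criteria are met again on the repeat test, a 24-hour urine sample will be collected".
- **Consequence, Section 11.12.1:** at 300 or more "mg/day, the patient will be referred to a nephrologist". Section 11.5 makes urinary protein of 300 mg/day or more, measured on a 24-hour collection, an adverse event of special interest.

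Section 9.15.1 also describes how voids are handled. After Screening, "patients will collect a first morning void urine sample on the date of the specified visit", the site does a dipstick, and an aliquot goes to the central laboratory. Table 3 gives the "laboratory analytes that will be measured for all urinalyses, including the first morning void urinalysis". Its urinalysis panel includes "Protein to creatinine ratio" and lists dipstick protein separately, as a test done by the site. The same section sends all blood and urine samples to the central laboratory unless noted otherwise, and adds: "The procedures for the collection, handling, and shipping of central laboratory samples will be specified in the Laboratory Manual".

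**The concern.** The repeat test and the criteria applied to it do not match. Two of the three criteria are UPCR limits, but the only repeat test named is a dipstick, which cannot show whether either limit is met again.

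The renal blood rule beside it has no such problem. For serum cystatin C and creatinine, "the test will be repeated within 1 week of the results", and the same limits are then re-applied to the same analyte.

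The kidney is the primary target organ in mice, rats and monkeys (Section 2.3.2.3), and safety, including urinalysis, is the primary objective. If sites read the rule differently across about 10 centers in about 6 countries, two patients with the same persistent rise in UPCR could be handled differently. One would get a 24-hour collection and could reach the mandated referral and the event of special interest; the other might not.

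**Working it through.** The plan states no figure to reproduce here. The check is a reading of the rule, with a little arithmetic on its limits.

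**1. Criteria against repeat test.**

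| Criterion | Measured by | Named in the repeat step? |
|---|---|---|
| Dipstick 2+ or more | Site dipstick | Yes |
| UPCR 0.5 mg/mg or more | Urinalysis panel, central laboratory | No |
| UPCR at least 2 x baseline | Urinalysis panel, central laboratory | No |

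**2. The UPCR limit that applies to a patient.** The two UPCR criteria are joined by *or*, so the lower one governs: limit = min(0.5, 2 x baseline). They cross at baseline = 0.5 / 2 = 0.25 mg/mg. The documents give no baseline values. At assumed baselines of 0.05, 0.10, 0.20 and 0.30 mg/mg the limits are 0.10, 0.20, 0.40 and 0.50 mg/mg. Below a baseline of 0.25 mg/mg the relative limit is the one that triggers.

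**3. Can UPCR be raised while the dipstick is below 2+?** I assume that a dipstick responds to protein concentration, whereas UPCR divides protein by creatinine. A UPCR of 0.5 mg/mg then corresponds to a protein concentration of 0.5 x urine creatinine:

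| Urine creatinine, mg/dL (assumed) | Protein at UPCR 0.5, mg/dL |
|---|---|
| 20 | 10 |
| 50 | 25 |
| 100 | 50 |
| 150 | 75 |
| 200 | 100 |

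One UPCR limit therefore spans a tenfold range of concentration (100 / 10) over this assumed range, so it cannot correspond to one dipstick grade. The documents do not say what concentration 2+ represents. This shows that the two tests can disagree, not how often they do.

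**4. Following the text literally.** A patient with an assumed baseline of 0.10 mg/mg has a UPCR at or above 0.20 mg/mg and a dipstick below 2+.

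- The rule starts, because a UPCR criterion is met.
- The dipstick is repeated within 1 week and is again below 2+. If nothing else is measured, no criterion is shown to be met again, and no 24-hour sample is required.
- At the next scheduled void (every 4 weeks from Week 5 to Week 49, Tables 1 and 2) UPCR is measured again. If it is still raised, the same step requires another dipstick.

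**5. With dipstick and UPCR on the repeat.** The same patient, with UPCR still at or above the limit, meets a criterion again and the 24-hour collection is required. The two readings part only when the repeat dipstick is below 2+ and UPCR is still raised.

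**The case against.** The strongest reply is that the protocol, read as a whole, already calls for UPCR on the repeat. Asking whether one or more of the criteria are met again makes little sense if only one can be assessed. Table 3 assigns its urinalysis panel, including UPCR, to first morning voids by sample type and not by visit. Section 9.15.1 sends urine samples to the central laboratory by default, and for scheduled voids the site dipstick is additional to the central aliquot. This stands as evidence of intent. A reader might infer that UPCR will not be re-measured, or that nothing in the protocol supports doing so; these provisions do not allow that conclusion.

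They do not settle the wording, however. The default has an exception for what is noted otherwise, and the dipstick is noted as a site test. The aliquot sentence concerns voids on the date of a specified visit. The repeat is called a dipstick, not a urinalysis.

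A second reply is that other safeguards exist, and this also stands in part:

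- Section 11.12.1 requires other potentially clinically significant urinalysis abnormalities to be confirmed at the following week's visit or sooner. Confirmed, clinically significant, treatment-emergent ones are recorded as adverse events, discussed with the medical monitor and followed with further tests or consultations if necessary.
- Confirmed clinically significant urinalysis abnormalities can be events of special interest (Section 11.5), which the DSMB reviews (Section 11.7.2).
- The investigator may repeat any laboratory test (Section 11.12).
- Later scheduled voids measure UPCR again.

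A reader might infer that a persistent rise in UPCR would go unnoticed, or that no specialist could be consulted. The documents do not support that. These provisions depend on clinical judgment or on the next visit, though, and none mandates the 24-hour sample.

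Finally, the Laboratory Manual is not among the documents and may define the repeat panel. That cannot be checked here.

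**Conclusion.** The point holds as a minor correction to a safety rule. It looks like a drafting omission, not a decision to confirm by dipstick alone. Followed literally, the rule mandates no 24-hour collection when UPCR stays raised with a dipstick below 2+. The mandated nephrology referral for proteinuria and the 300 mg/day event of special interest would then not be reached by this route.

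The effect is confined to individual safety follow-up and to consistent ascertainment of that one event. Its frequency cannot be estimated: the documents give neither baseline UPCR nor the rate at which the two tests disagree.

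A reader might infer that the primary safety analysis is compromised. The documents do not support this. Sections 12.5.1 to 12.5.3 plan no summary by event of special interest, and urinalysis results are still summarized and abnormalities listed under Section 12.5.2.

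A reader might also recall the false-positive urine protein results in the Phase 1 study (Section 2.3.3) and infer that dipsticks are unreliable with this drug. That interference concerned a pyrogallol red dye-binding method on 24-hour pooled urine; the protocol reports none for dipsticks.

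The conclusion assumes that the Laboratory Manual does not already require UPCR on the repeat void.

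**What to change.** In Sections 9.15.1 and 11.12.1, change the repeat step to read: *first morning void dipstick protein and central-laboratory UPCR will be repeated within 1 week; if any of the three criteria is met again, a 24-hour urine sample will be collected.* Check that the Laboratory Manual agrees.

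The cost is one sentence in two sections and one central-laboratory aliquot per triggered repeat, taken from a void that is being collected anyway. There may be a few more 24-hour collections, which are a burden for patients and caregivers. Sample size, endpoints and the analyses in Section 12 stay as they are.
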